#### **IV. Inclusion/Exclusion Criteria**

##### **Eligibility**

The eligibility criteria listed below will be assessed at the recruitment visit.

Inclusion Criteria	Exclusion Criteria

 
◆ Age 18 years or older
 
◆ Currently enrolled at a Tribal college
 
◆ Have a valid telephone number and email address
 
◆ Willing to participate in all study components
 
◆ Willing to be followed-up for 6 months
 
◆ Self identifies as American Indian or Alaska Native
 
◆ Is a current smoker – self defined
 
	
 
◆ Planning to leave the college within next 6 months
 
◆ Medically ineligible as a result of screening questions
 

Medical Exclusion Criteria

For overall participation
 
 
◆ Medically ineligible as a result of screening questions
 
◆ Participant under the age of 18 years
 

For NRT (Patch, gum, lozenge):
 
 
• History of severe eczema or any serious skin problem if requested nicotine patch
 
• History of severe allergic reaction to the nicotine patch or other skin adhesives
 
• History of heart attack in the last 2 months
 
• Currently experiencing frequent angina or chest pain related to heart
 
• Currently experiencing signs and symptoms of peptic ulcer
 
• Currently receiving medications for rapid or irregular heart beat
 
• Currently experiencing signs and symptoms of severe, uncontrolled high blood pressure
 
 
For Chantix:
 
 
• Pregnant or breast feeding or planning to become pregnant in the next 6 months
 
• Currently using nicotine replacement therapy (NRT)
 
• History of suicide attempt in the past 12 months
 

- History of thoughts of suicide in the past 12 months
- History of thoughts of harming others in the past 12 months

For Zyban:

- Pregnant or breast feeding or planning to become pregnant in the next 6 months
- History of seizure disorder or head trauma
- History of severe allergic reaction to Zyban (also known as Wellbutrin, Bupropion)
- History of eating disorder, such as anorexia or bulimia, which is overeating and throwing up
- Currently taking Wellbutrin, Zyban or any other medications that contain bupropion
- History of alcohol or substance abuse in the past year
- Current excessive alcohol consumption defined as 14 or more alcoholic drinks per week and / or binge drinking ( 5 or more drinks on one occasion) 2 or more times in the past month
- Use of MAO inhibitors, such as Nardil, tranylcypromine, phenelzine, or Parnate
- Reported use of illegal drugs (opiates, cocaine, narcotics, or other stimulants such as diet pills)
- Use of psychoactive medications, such as fluoxetine, doxepin, clonidine, or buspirone
- Use of benzodiazepines, such as Xanax, Valium, Ativan, Klonopin in the past 2 weeks

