## **Risks**

Most of the risks involved in the study relate to adverse events related to study medication. Chantix and bupropion are both approved by the Food and Drug Administration as an aid for smoking cessation. The most common adverse events associated with bupropion are headache, insomnia, rhinitis, dry mouth, and anxiety. Bupropion is associated with an increased risk (1/1000 at 300 mg/day) of seizures (GlaxoSmithKline, unpublished data). We will minimize this risk by screening out and preventing participants from using bupropion who are also currently using any additional form of bupropion, psychoactive medications, nicotine replacement therapy, fluoxetine, clonidine, buspirone, or doxepin in the past 30 days and those with: self-reported alcohol dependence within the past year; history of seizures or head trauma; history of bulimia or anorexia nervosa; pregnant (as measured by over the counter pregnancy test kit for women of child-bearing age only) or contemplating pregnancy; breast feeding; myocardial infarction in the past 30 days, and use of other forms of tobacco in the past 30 days. The most common adverse events associated with Chantix are nausea, changes in dreaming, constipation, gas, and/or vomiting. The FDA recently required new boxed warning for both these medications: people who experience any serious and unusual changes in mood or behavior or who feel like hurting themselves or someone else stop taking the medication. Chantix has no clinically meaningful drug interactions based on drug characteristics and clinical experience with the drug to date (Pfizer).

All participants requesting prescription medications, Chantix or Bupropion will be screened and medically cleared by the on-the-ground primary care physician. [name] will continue his role as reviewing study physician. [name] will provide secondary review of all screeners, and intake materials to make sure there are no contradictions to pharmacotherapy. We have a long track record of [name] reviewing all medication screeners and study documents on

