- Individual In-Person Visit (Randomization):** Potential participants will meet with a research assistant on campus. At this initial in-person visit, the research assistant will have randomization assignments with them so they can inform the participant which arm they have been randomized to for this program. This session will allow research assistants to explain the program and answer any questions the participant may have that he or she may have about the program. Informed consent will also be obtained during this visit. Finally, it allows the research assistant to explain NRT or pharmacotherapy and provide each participant with information. Individuals who consent to participation will be enrolled in the program and will remain in the arm to which he/she is randomized to for the study. Research assistants will collect baseline saliva sample from each participant. Participants will be informed for future samples (week 12 and month 6), we will request mailings of saliva samples so they will be taught how to provide such samples at this baseline visit. Saliva sample kits will be provided via overnight mail with a pre-paid overnight return. Members of our team have used this approach in other phone-based smoking cessation programs with success. Participants will be asked to make a decision about NRT or pharmacotherapy prior to the second web session. Facilitators will answer any questions the participant has and participants will be given the option of having the study physician call them to discuss personal concerns. Estimated time for individual session is 50-60 minutes. Participants who have not yet decided on medication will be asked to do so then. All participants requesting any form of pharmacotherapy will complete the corresponding medical screener. The study physician will review all medical information prior to the first session. After taking part in the initial session, participants will be e-mailed a login to the website prior to their first session. Future surveys will be done via web interface.

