### **Plans for Assuring Compliance with Requirements Regarding the Reporting of Adverse Events (AE).**

The pharmacotherapy that will be used in this study has been approved by the Food and Drug Administration for aid in smoking cessation treatment. The adverse events associated with the TNP are few and mild and include skin irritation at the patch site and mild increases in heart rate and blood pressure. Adverse events related to nicotine gum and lozenge use are generally few and mild and can include hiccups, sore mouth and jaw, indigestion, headache, nausea, and insomnia. Studies have shown that varenicline is well tolerated, with few and mild adverse effects. The most common varenicline-related adverse effect is nausea, which is reported to be mild to moderate. Varenicline use will be monitored by the patient's primary care physician. The most common adverse effects associated with bupropion are dry mouth and insomnia. Subjects may also rarely complain of confusion, anorexia, or dizziness. Bupropion is also associated with a 1/1000 risk of seizures at the dose that will be used in this study. Factors that may increase the risk of seizures include: a history of head trauma, seizures, CNS tumors, excessive use of alcohol or cocaine, withdrawal from alcohol or benzodiazepines, and use of certain other drugs, including antipsychotics, antidepressants, theophylline, and systemic steroids. All patients will be screened for risk factors for seizures prior to recommending use of bupropion. Bupropion will only be provided to participants who have received a prescription from their primary care physician.

Participants will be prompted to discuss any adverse effects with their primary care physician or, if they do not have a primary care provider, with [name] or the on-site clinician who will work with [name]. Both subjects and physicians will be given the study office phone number (24-hour coverage) to contact study staff and/or investigators to report adverse events.

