## **Suicide/Homicide Procedures**

Serious neuropsychiatric symptoms have occurred in patients taking Chantix. These symptoms include changes in behavior, agitation, depressed mood, suicidal ideation, and attempted and completed suicide. While some patients may have experienced these types of symptoms and events as a result of nicotine withdrawal, some patients taking Chantix who experienced serious neuropsychiatric symptoms and events had not yet discontinued smoking. In most cases, neuropsychiatric symptoms developed during Chantix treatment, but in others, symptoms developed following withdrawal of Chantix therapy.

As a result, special caution must be taken if a participant reports an *increase in depressed mood, agitation, changes in behavior not typical for them, or **suicidal thoughts or action** since starting the study medication*. The suicide/homicide protocol will be instituted for all participants noting changes of this sort since starting Chantix.

The suicide/homicide protocol is as follows:

1. Ask participant to describe their symptoms in more detail.

*“Tell me more about what you are experiencing.”*

2. Assess the level of severity.

*“In general, would you say these symptoms are mild, moderate or severe?”*

3. Assess attribution of symptoms to the study medication.

*“Do you believe these symptoms are caused by the study medication or another cause?”*

4. Assess suicide/homicide risk

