### Course of Action

1. If a participant reports **any** suicidal/homicidal ideation, including passive ideation (e.g., thoughts of death, would be better off dead, doesn’t care about living, etc.) or active ideation (has intent to harm, a plan, and means) advise them to stop taking the medication immediately.
2. If the participant is exhibiting active suicidal or homicidal ideation and DOES intend to harm him or herself or someone else:
  - a. Each local mental health center office provides 24 hour a day telephonic crisis response for any citizen in crisis. After discussing the person's problems on the phone the mental health professional (MHP) will decide whether a face to face evaluation is needed.
  - b. Where full time dedicated MHP teams exist, emergency crisis services are available to all persons for both telephone crisis support and face to face evaluations, where clinically indicated, on a 24/7 basis. In offices without dedicated full time crisis teams, clinicians are on call to respond to emergency requests for evaluation and dispositions only for WMMHC clients.
  - c. When a person is judged not to be in an emergency situation, as defined in Montana statute, the person may be given an emergency appointment at the local center for the next day, or referred to a local hospital for voluntary psychiatric admission, or linked with other community resources as appropriate.
  - d. If the individual has a primary therapist, who is not affiliated with the mental health center, that primary therapist will be contacted as soon as practical by the MHP.

- e. Stay with the participant until the crisis worker is able to intervene.
3. If the participant is exhibiting passive suicidal or homicidal ideation and does NOT intend to harm him or herself, the counselor should provide the participant with the **Mental Health Resource Card** and the **Crisis Referral List**. The counselor should also encourage the participant to seek support from friends, family, and possibly mental health resources.
4. If there is no suicide risk but the participant reports neuropsychiatric symptoms (increase in depression, change in mood, agitation, etc.) that are more than mild and that they attribute to the study medication, advise them to stop taking the medication immediately.

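### The suicide/homicide procedure is triggered only by changes since starting Chantix, although the protocol states the same boxed warning for bupropion

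*Protocol*

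**What the plan says.** **Warning.** Section III (Risks) discusses Chantix and bupropion together and says: "The FDA recently required new boxed warning for both these medications". The instruction that follows is to stop the drug on serious, unusual mood or behavior change, or on feeling like hurting oneself or someone else.

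**On-treatment procedure.** Section VI, Suicide/Homicide Procedures, gives a rationale that names only Chantix. It then calls for special caution over mood, agitation, behavior or suicidal changes "since starting the study medication". The next sentence reads: "The suicide/homicide protocol will be instituted for all participants noting changes of this sort since starting Chantix". Under Course of Action, a participant who reports any suicidal or homicidal ideation is to be told to stop ("advise them to stop taking the medication immediately"), with no drug named. Bupropion is not named anywhere in the procedure.

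**History before treatment.** Section IV lists, under Chantix, "History of suicide attempt in the past 12 months", together with thoughts of suicide and thoughts of harming others over the same period. The Zyban list has none of the three. The bupropion screening text in Section III does not mention them either, and the one in Section VI concerns seizures: "All patients will be screened for risk factors for seizures prior to recommending use of bupropion".

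**How screening is done.** Section IV states: "The eligibility criteria listed below will be assessed at the recruitment visit". The description of the in-person randomization visit in Section V states: "All participants requesting any form of pharmacotherapy will complete the corresponding medical screener".

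**The concern.** A safety procedure should start for every participant exposed to the risk it addresses. The protocol says the risk attaches to two drugs, and both arms are offered both. The sentence that starts the structured assessment (severity, attribution, ideation, plan, means, history) and the crisis steps names one of them. Staff who follow the text literally would not begin the procedure for a bupropion user whose mood deteriorates. Staff who do begin it would be departing from the stated trigger.

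The eligibility lists add a lesser worry. A student barred from Chantix because of recent suicidality may turn to bupropion, and nothing in the text says that this history would reach the clearing physician. The stake is participant safety: the event is rare but grave.

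**Working it through.** The protocol gives no figure on this point, so the check sets the texts side by side.

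| Step | Chantix user | Bupropion user |
|---|---|---|
| Boxed warning (III, Risks) | Yes | Yes |
| Special-caution sentence (VI) | Yes | Yes, since it refers to study medication |
| Sentence starting the procedure (VI) | Yes | No |
| Stop and referral steps (VI, Course of Action) | Yes | Worded neutrally, but they are steps of the procedure whose trigger names Chantix |
| 12-month suicidality and harm-to-others items (IV) | Listed as exclusions | Not listed |
| Added tribal-clinic monitoring (III) | Stated | Not stated |

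**Trigger.** The caution sentence and the trigger sentence are adjacent and describe the same symptoms, yet differ in the drugs covered. No reason is given for the narrowing, and it does not match the warning as Section III states it.

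**Do other safeguards lead a bupropion user into the procedure?**
- Physician clearance and secondary review (III) and the prescription requirement (VI) act mainly before treatment. The reviewing physician also follows up reported side effects, but no route to the procedure is stated.
- The three weekly questions (III) cover side effects, urgent visits and new health problems, with phone follow-up. None names mood or self-harm.
- Weekly contact with a campus clinician or nurse (III) reviews adverse events for any drug, again with no stated link.
- The Section VI inquiry starts from an urgent, emergent or unexpected medical encounter, not from a mood change.
- The CES-D and PANAS negative affect are scheduled for all participants at weeks 1, 3, 5, 7 and 12 and month 6 (Measures table). No action is tied to a score.

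Each narrows the gap. None closes it by rule.

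**History items.** Section IV suggests that all listed criteria are assessed for everyone. Section V ties medical screening to the form for the drug requested. Whether bupropion requesters are asked is therefore unclear, and the forms are not shown.

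**Workload of asking them.** The documents give neither bupropion uptake nor the prevalence of this history. Assume, for illustration only, that 10% to 30% of the 300 participants request bupropion and that 2% to 10% of those have such a history:
- Requesters: 300 × 0.10 = 30 to 300 × 0.30 = 90.
- Positive answers: 30 × 0.02 = 0.6 to 90 × 0.10 = 9.

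These figures size the extra questions and reviews. They do not count students who would worsen or be harmed, and they make no allowance for students already removed by other Zyban exclusions or by physician clearance.

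**The case against.** The strongest defense is that the trigger wording is a slip with little consequence. The phrase about changes of this sort refers back to the drug-neutral caution, the Course of Action speaks of any participant and any ideation, and it requires a case note and immediate physician contact whatever the level of threat. Section III also states the stop rule for bupropion. This largely answers one tempting reading, that a bupropion user who voices suicidal thoughts has no stop rule or no protection at all. The documents do not support that reading. What stands is that the sentence deciding who enters the procedure excludes that user.

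A second tempting reading is that leaving the three history items off the Zyban list is itself an error, or that bupropion requesters are not asked about suicidality. Neither is supported. The warning is an instruction to stop if symptoms appear, so the two drugs need not share exclusions. The screener forms are not available, clearance and secondary review apply to both prescription drugs, and medical ineligibility on screening questions is a general exclusion. The Zyban bars on psychoactive drugs, recent benzodiazepines, substance abuse, heavy drinking and eating disorders may also remove some students at risk. The objection succeeds here to the extent that this part is an improvement to offer and not a fault shown.

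The contrast over tribal-clinic monitoring should not be pressed either, since weekly web monitoring and weekly clinician contact are not limited to Chantix.

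**Conclusion.** The point holds for the trigger. Within Section VI, and against the warning in Section III, the protocol limits the start of its suicide/homicide procedure to Chantix users and leaves bupropion users with the same symptoms outside it. The general safeguards lessen the consequence without supplying the missing route. This should be corrected.

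The history questions are a secondary, low-cost improvement. The conclusion assumes nothing about the content of the screener forms.

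The number of students affected cannot be derived from the documents. The illustrative 0.6 to 9 rests wholly on assumed uptake and prevalence, so it should not be read as expected harm or used to argue severity. Sample size, randomization and the primary analysis are unaffected.

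**What to change.** 1. **Main change.** In Section VI, Suicide/Homicide Procedures, reword the trigger so that it covers changes *since starting Chantix or bupropion*. The cost is a short amendment and a note to staff.
2. **Secondary change.** State that the three 12-month history questions already used for Chantix are also asked of students who request bupropion, and that the local and reviewing physicians see the answers before clearance. A positive answer should lead to physician judgment and closer follow-up if needed, not automatic exclusion. The cost is three more questions per bupropion requester (30 to 90 students under the assumed uptake) and a few more physician reviews (up to about 9 under the same assumptions).

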## **V. Study Procedures**

### **Design Overview**

The proposed study is a randomized design in which Tribal College smokers will receive one of two internet-based interventions: 1) a culturally and individually tailored, interactive smoking cessation intervention (**I-ANBL**); or 2) internet-based healthy diet -fruit and vegetable consumption intervention (**I-FV**). Participants in both groups (I-ANBL and I-FV) will be offered pharmacotherapy (e.g. varenicline or bupropion or NRT). The primary outcome of interest will be biochemically verified continuous abstinence at 6 months. Secondary endpoints include number of quit attempts and number of cigarettes smoked (among continuing smokers), pharmacotherapy utilization, and the number of completed web-sessions. We will also examine the marginal cost-effectiveness of the intervention.

We propose the adaptation and testing of a culturally tailored smoking cessation program for tribal college students. We will finish developing the program using an iterative, CBPR process that we have used in the past to develop a successful smoking cessation program for AI.

The study will be done in three phases over a five-year period. Phase 1 will include adaptation of the program and tailored materials, including assessments of the website for scientific

accuracy, readability, cultural appropriateness, and navigability; Phase 2 will be to conduct the randomized trial and Phase 3 will consist of data analysis and dissemination.

Participants will be recruited from a Tribal college.

**Pharmacotherapy:** The PI of this study along with our AI community members agreed that all participants (I-ANBL and I-FV arms) had to be offered pharmacotherapy (varenicline or bupropion or NRT) as a component of the study design. This decision was a collaborative one between the AI tribes and the investigators who have worked with this population. The AI community will not accept placebo treatment, therefore, the interventions would not be acceptable or feasible to potential participants if a placebo was part of the study design.

**Implementation Plan**

The project will be implemented in three phases over five years, as summarized in the table. The main purpose of this study is to determine the effectiveness of an internet-based culturally-tailored smoking cessation program for tribal college smokers.

Phase 1: Development and Training	Development and assessment of interactive website; training of staff; focus groups and pre-testing, conduct meetings with CAB, submit any protocol modifications for community and IRB approval	Year 1
Phase 2: Deliver Intervention	Recruitment of tribal college smokers into study, baseline measurements, randomization of eligible students, implementation of internet-based intervention, follow-up, preliminary data cleaning, and initial data analysis	Year 2 – Year 4
Phase 3: Data analysis and dissemination	Post-intervention assessments; final data cleaning and analysis; manuscript preparation; presentations to communities and at professional conferences	Year 5

